6.2 Recruitment rate

Trial centres will be recruited in a staggered way, bringing on 3 centres in each of months 4 and 5, and then 6 or 7 centres per month during months 6 through 13, making a total of 58 centres (8 in menu A:O:R; 10 in menu A:R, and 40 in menu O:R). Steady state will be achieved by month 11 for the two menus involving arthroscopy, and by month 13 for the O:R option. We anticipate having in aggregate 188 centre months for A:O:R (steady state monthly rate of 9 to achieve 210 participants), 233 centre months for A:R (steady state monthly rate 10 to achieve 240 participants), and 856 centre months for O:R (steady state monthly rate 11 to achieve 240 participants), or 690 randomised participants in total. The Hospital Episode Statistics data for 2004/2005 indicates that 1295 rotator cuff repairs took place in NHS hospitals in England alone giving a mean of 15 per trust. With fifty eight centres recruited there is a potential recruitment rate in the order of 75 patients per month. In steady state we will need to be recruiting 30 patients per month, or 40% of the available throughput. Expected recruitment milestones will be 16 (month 6); 142 (month 12); 320 (month 18); 507 (month 24) and 690 (month 30).

Participant recruitment

We anticipate that the trial will require the participation of 58 centres. If the recruitment of patients is failing to meet targets and cannot be increased at participating centres then we would increase the number of centres in the trial.

7. ORGANISATION

7.1 In summary

A detailed plan and timetable of study organisation is given in the Gantt chart (Appendix VI). In summary, it is as follows – 1-4 months: set up office, assemble team, obtain ethical approval and establish first centre; 5-13 months: establish study in all centres; 4-30 months: identify and recruit participants into the study; 12-38 months: 8 month post-randomisation follow-up complete; 16-42 months: 12 month post-randomisation follow-up complete, including one year post-operative MRI scan; 28-54 months: 24 month post-randomisation follow-up complete and database closure; 54-60 months: complete data collection, analysis and dissemination.

7.2 Local organisation in centres

The trial is designed to limit the extra work required by the collaborating clinicians to tasks that only they can do. The research teams in Oxford and Aberdeen will facilitate the trial remotely and initiate site visits as required.

7.2.1 Lead consultant surgeon

Each collaborating centre will identify a lead consultant surgeon who will be the point of contact for that centre. The responsibility of this person will be to:

- establish the study locally (e.g. facilitate local research ethics committee approval, liaise with the local R&D manager and inform all relevant local staff about the study)
- take responsibility for the conduct of the research locally
- notify the study office in Oxford of any unexpected clinical events which might be related to study participation
- provide support and supervision for the local research nurse if applicable
- represent the centre at UKUFF collaborators meetings
- initiating recruitment of participants
- maintaining communication with the study office in Oxford regarding allocated surgical treatment, date of operation, discharge instructions and surgery withdrawal
-

7.2.2 Research nurse (if applicable)

Some centres will identify a research nurse to organise the recruitment of the participants. The responsibility of this person will be to:

- keep regular contact with the lead consultant surgeon and notify them of any problem or unexpected development
- maintain regular contact with the study office
- keep local staff informed of the progress of the study
- assist the lead surgeon to inform the participants about the study and answer any questions they may have
- obtain written consent from the participant
- supply participant with the invitation letter, full consent form (if applicable), baseline questionnaires and a pre-paid envelope for their return to the study office in Oxford
- represent the centre at collaborators meetings

7.3 Central organisation of the study

Reflecting the complex nature of the trial, trial functions will be divided between the Oxford coordinating team and the Aberdeen coordinating team.

7.3.1 Study co-ordination in Oxford

The UKUFF study team in Oxford is divided between the Nuffield Department of Orthopaedic Surgery (NDOS) and the Department of Public Health and Primary Care (DPHPC). Both departments are a part of the University of Oxford with NDOS having very strong links with the Nuffield Orthopaedic Centre NHS Trust.

7.3.1.1 NDOS

The NDOS team will be responsible for all clinical aspects of the trial including; the recruitment and education of surgeons, recruitment of participants, the coordination of the Rest then Exercise Programme, daily management and troubleshooting of clinical issues from staff and participants in the trial and the coordination of the 12 month post operative MRI scans.

7.3.1.2 DPHPC

The UKUFF team in DPHPC are responsible for the design, conduct and analysis of the concurrent economic evaluation and outcome questionnaires.

7.3.1.3 Timing of meetings

All members of the management team in Oxford will aim to meet quarterly to review trial progress. NDOS members will aim to meet weekly to discuss site, surgeon and patient recruitment.

7.3.2 Study co-ordination in Aberdeen

The Aberdeen team are based at the Centre for Health and Randomised Trials within the Health Services Research Unit at the University of Aberdeen. They will be responsible for all data aspects of the trial including: the design and set-up of trial databases, the randomisation system, the management of postal participant follow-up, data management and verification and the conduct of final trial analysis.

7.3.2.1 Timing of meetings

The management team in Aberdeen will meet weekly and a conference call with the CI and trial coordinator in Oxford will occur fortnightly.

7.3.3 Production of reports

The production of all interim reports for the trial steering committee, data monitoring committee, and progress reports required by the funding body, sponsor and ethical committees will be completed in collaboration with all teams and coordinated by the trial managers in Oxford and Aberdeen.

7.4 UKUFF Management Group

The trial management group will oversee all aspects of the conduct and progress of the trial and ensure that the protocol is adhered to. They will be responsible for the daily management

of the trial and will meet at 6 monthly intervals to review the progress of the trial. The group consists of the grant holders and representatives from both the study office in Oxford and Aberdeen.

7.5 UKUFF Steering Committee

The study is overseen by an independent Steering Committee. The chairman is [name], with [name] and [name] acting as the other independent members. The study grant holders, along with [name], complete the Steering Committee. This committee will meet annually or more frequently if circumstances dictate. They will take responsibility for any major decisions, such as the need to close recruitment or more parts of the study or to change the protocol for any reason.

7.6 Data and Safety monitoring

7.6.1 UKUFF Data Monitoring Committee

The Data Monitoring Committee is independent of the study organisers. The chairman is [name], a Reader in Orthopaedic Surgery, along with [name] (Reader in Physiotherapy) and [name] (Senior Lecturer in Medical Statistics). During the period of recruitment to the study, interim analyses will be supplied, in the strictest confidence, to the data monitoring committee, together with any other analyses that the committee may request. This may include analyses of data from other comparable trials. In light of these interim analyses, the Data Monitoring Committee will advise the Steering Committee if, in its opinion, the trial has provided both:

- a) proof beyond reasonable doubt that for all or some types of participants one intervention is clearly indicated in terms of clinical and cost effectiveness
- b) evidence that might reasonably be expected to influence materially the care of the people with rotator cuff tears by clinicians who know the results of this and comparable trials.

The Steering Committee can then decide whether or not to modify intake to the trial. Unless this happens, the Steering Group, Management Group, consultant surgeons and study office staff (except those you supplied the confidential analyses) will remain ignorant of the interim results.

The frequency of the interim analyses will depend on the judgement of the Chairman of the committee, in consultation with the Steering Committee.

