5.4 Economic evaluation

A cost-effectiveness analysis will be performed. A simple patient cost-related questionnaire will be sent out at baseline and at 12 and 24 months post randomisation, to obtain information on primary care consultations, other consultations, out-of-pocket costs, work-impact of the intervention received and return to work. Unit costs will come from national sources and participating hospitals. The patient questionnaire will also be used to administer the EQ-5D, which will also be obtained at baseline. The main health economic outcome will be within-trial and extrapolated quality adjusted life-years, estimated using the EQ-5D.

Incremental cost-effectiveness will be calculated as the net cost per quality-adjusted life year gained, for arthroscopic surgery versus Rest then Exercise, open surgery versus Rest then Exercise, either surgical versus Rest then Exercise and arthroscopic surgery versus open surgery. Power calculations (see following section) are based on clinical rather than cost-effectiveness outcomes, which will be estimated rather than used in hypothesis testing. Cost-effectiveness ratios and net-benefit statistics will be calculated. We will report within-trial cost-effectiveness; if the trial produces sufficient evidence to plausibly model future quality of life or costs (e.g. based on projected failure rates) we will also extrapolate long-term cost-effectiveness beyond the trial period.

An important component of this trial will be assessment of cost. Therefore, an accurate record of procedures at each of the proposed centres is essential. To evaluate costs of each type of surgery, information from the operating theatres will be collected. Theatre managers will be contacted and visited at each site. Resources used, equipment costs and standard procedures

for rotator cuff repairs will be looked at. Per case information will also be analysed. A checklist of equipment, consumables, implants, time and staff utilized during each case will be completed by theatre staff. Information from theatres will be collected by the Oxford UKUFF office and used in a cost comparison between the arthroscopic and open surgery.

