7.6.2 Safety concerns

The UKUFF trial involves three interventions that are well established in clinical practise, although unproven for clinical and cost effectiveness. Two of these interventions are surgical and so inevitably there are safety concerns surrounding them. These include:

- surgical site infection
- frozen shoulder
- complications relating to anaesthetic and or theatre equipment
- uncontrolled bleeding

As the techniques are standard treatments for rotator cuff tears, and because the surgeons are performing their usual and preferred surgical procedures, the trial participants would not be

put at any more risk than is normally associated with the treatment. It is anticipated that none of these events would be classified as a serious adverse event but we would respond appropriately to any notification (Appendix VII).

Collaborators and participants may contact the chairman of the Steering Committee through the trial office in Aberdeen or Oxford about any concerns they may have about the trial. If concerns arise about procedures, participants or clinical or research staff (including risk to staff) these will be relayed to the Chairman of the Data Monitoring Committee.

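### The one stated criterion for Data Monitoring Committee advice on interim results needs both clinical and cost-effectiveness proof and names no harm ground

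*Protocol*

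**What the plan says.** Protocol section 7.6.1 supplies confidential interim analyses to the DMC while recruitment is open, with any further analyses it asks for. It then sets the condition for advice: "the Data Monitoring Committee will advise the Steering Committee if, in its opinion, the trial has provided both" of two things. Limb (a) is "proof beyond reasonable doubt that for all or some types of participants" "one intervention is clearly indicated in terms of clinical and cost effectiveness". Limb (b) is "evidence that might reasonably be expected to influence materially the care of the people with rotator cuff tears" by clinicians who know the results.

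On the consequence, the section says: "The Steering Committee can then decide whether or not to modify intake to the trial". Unless that happens, the Steering Group, the Management Group, the surgeons and most office staff "will remain ignorant of the interim results".

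Four other places bear on this:
- Section 7.6.2 lists surgical safety concerns. Of concerns about procedures, participants or staff it says that "these will be relayed to the Chairman of the Data Monitoring Committee".
- Section 7.5 makes the Steering Committee responsible for major decisions, including closing recruitment.
- Section 5.4 says of the cost-effectiveness outcomes, "which will be estimated rather than used in hypothesis testing".
- Section 5.3 has the DMC agree its terms of reference early in the trial. These are listed as Appendix XI, and safety reporting as Appendix VII. Neither text is in the document at hand.

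**The concern.** Section 7.6 covers data and safety monitoring together, yet the only criterion it writes down for DMC advice concerns benefit. Limb (a) speaks of an intervention being indicated. Neither limb mentions complications, harm or an arm being contraindicated.

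Limb (a) also joins clinical and cost effectiveness with *and*, at a very high standard of proof. A clear clinical difference is therefore not enough without an equally clear economic one.

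The DMC is the body that sees outcomes by arm. If it follows the section as written, it has no stated ground for reporting an excess of harm, and the body able to change intake would not be shown that excess. Two of the three arms are surgical, and surgical complications are a listed secondary outcome (section 5.1).

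**Working it through.** The protocol gives no figure to reproduce here. The check is of the rule's logic, followed by a count of the data available.

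**Logic.** Advice is triggered if (a) and (b) both hold, and (a) needs clinical proof and cost-effectiveness proof.

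| Interim finding | Clinical part of (a) | Cost part of (a) | Criterion met? |
|---|---|---|---|
| Excess harm in one arm, no arm shown better | not met | not met | no |
| Excess harm so large that another arm is arguably indicated | arguably met | not shown | no |
| Clear clinical benefit, cost effectiveness uncertain | met | not shown | no |
| Clear clinical benefit and clear cost effectiveness | met | met | yes, if (b) also holds |

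The second row matters. Even the most generous reading of *indicated* leaves the cost part outstanding.

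**Other possible routes.** Section 7.6.2 brings concerns to the DMC Chairman but states no criterion or action that follows. Section 7.5 gives the Steering Committee power to act, but 7.6.1 keeps it from the interim results unless the advice route is followed. The DMC's right to request analyses gives it data, not a ground for advice.

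**Data available for the cost part.** Inputs:
- Recruitment runs over months 4 to 30 (section 7.1).
- Milestones are 16 randomised by month 6, 142 by month 12, 320 by month 18, 507 by month 24 and 690 by month 30 (section 6.2).
- Patient cost questionnaires are sent at baseline, 12 and 24 months (section 5.4).

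The number that can have reached 12 months at calendar month *m* is the number randomised by month *m* − 12. For 24 months it is the number randomised by month *m* − 24.

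| Month | Randomised | Reached 12 months | Reached 24 months | Still to randomise |
|---|---|---|---|---|
| 18 | 320 | 16 (16/690 = 2.3%) | 0 | 690 − 320 = 370 |
| 24 | 507 | 142 (142/690 = 20.6%) | 0 | 690 − 507 = 183 |
| 30 | 690 | 320 (320/690 = 46.4%) | 16 (16/690 = 2.3%) | 0 |

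These are upper limits. With the 10% attrition expected in section 6.1, 320 becomes 320 × 0.9 = 288. The 46% is reached only when no intake is left to modify. At month 24, with 183 places open, at most 21% of the planned total could have 12-month cost data and none 24-month data. Theatre costs are recorded at operation and come sooner, but they cover only part of the comparison.

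**The case against.** The strongest reply is that 7.6.1 says the DMC will advise *if* both limbs are met, not *only if*. That fixes when advice is due and does not forbid other advice. This stands. A reader might infer that the DMC is barred from raising harm, and the text does not say so. The sentence keeping the Steering Committee unaware of interim results does, however, favour reading the criterion as the intended route.

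A reader might also infer that the trial lacks safety oversight. The document does not support that. Section 7.6.2 gives a route for concerns, 7.5 gives a general power, and Appendix VII or XI may hold a harm criterion. What remains is narrower: the visible section states a rule that omits harm, and if an appendix is wider the two need reconciling.

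Nor is there a flat contradiction with section 5.4. Estimating cost effectiveness without testing it is compatible with a committee forming an opinion on it. Section 5.4 shows only that the trial is not powered for the proof limb (a) asks for.

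The timing counts should not be pressed too far. To call the cost part unreachable would be a judgement, since no effect size or variance is given. The shortage of 24-month data applies equally to the primary outcome, the Oxford Shoulder Score at 24 months. And the 380 participants allocated to surgery (2 × (70 + 120), Table 1) are simply the planned allocation, not a measure of exposure caused by this wording.

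**Conclusion.** The point holds as a defect in a rule the protocol states, not as a complaint about missing detail. Under 7.6.1 as worded, neither comparative harm in one arm nor clear clinical benefit without cost-effectiveness proof meets the criterion for DMC advice. The economic part is hard to satisfy while intake can still be changed: at most 142 of 690 with 12-month patient cost data at month 24, and 320 of 690 with 12-month and 16 of 690 with 24-month data at month 30.

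This rests on recruitment meeting its milestones and on the visible text alone. If Appendix VII or XI already makes harm a ground for advice, what is left is an inconsistency between 7.6.1 and that appendix. The change should be made because it bears on participant safety and costs little. The document does not show that harm would in fact go unreported.

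**What to change.** Amend section 7.6.1 in two respects:

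1. Let limb (a) be satisfied when an intervention is clearly indicated or clearly contraindicated on clinical outcome, with cost effectiveness as supporting information and not as a condition.
2. State that evidence of harm in any arm is by itself a ground for advice to the Steering Committee, without limb (b).

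Cross-refer to section 7.6.2, so that it is clear what may follow once a concern reaches the DMC Chairman, and bring the section into line with the DMC terms of reference and the safety reporting appendix. Any threshold is for the committees to set.

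The cost is one or two sentences and matching words in the terms of reference. No new data are needed. The downside is slightly broader grounds for DMC advice, and so somewhat more reliance on the committee's judgement.

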7.6.2 Safety concerns

The UKUFF trial involves three interventions that are well established in clinical practise, although unproven for clinical and cost effectiveness. Two of these interventions are surgical and so inevitably there are safety concerns surrounding them. These include:

- surgical site infection
- frozen shoulder
- complications relating to anaesthetic and or theatre equipment
- uncontrolled bleeding

As the techniques are standard treatments for rotator cuff tears, and because the surgeons are performing their usual and preferred surgical procedures, the trial participants would not be

put at any more risk than is normally associated with the treatment. It is anticipated that none of these events would be classified as a serious adverse event but we would respond appropriately to any notification (Appendix VII).

Collaborators and participants may contact the chairman of the Steering Committee through the trial office in Aberdeen or Oxford about any concerns they may have about the trial. If concerns arise about procedures, participants or clinical or research staff (including risk to staff) these will be relayed to the Chairman of the Data Monitoring Committee.

7.6.3 Data handling and record keeping

All data collected and stored as a result of the study will comply with the data protection act.

8. FINANCE

The UKUFF trial is funded by the UK NHS Health Technology Assessment Programme (Ref: 05/47/02). The Nuffield Department of Orthopaedic Surgery in Oxford will manage the finances and budget.

Participating sites will be asked to invoice the UKUFF study quarterly in order to receive the payment of £200 per randomised patient. The trial coordinator will supply each site with their recruitment numbers at the end of each quarter so the invoice can be raised for the correct amount.

Participating sites will also be asked to invoice the UKUFF study quarterly in order to receive the payment for the required MRI scan. The cost of these scans will be negotiated with each site before the first scan is undertaken. This cost is entered into the Clinical Trial Agreement implemented between the site and the University of Oxford.

9. SATELLITE STUDIES

The funds provided by the HTA Programme are to conduct the main trial as described in this protocol. Nevertheless, it is recognised that the value of the UKUFF trial will be enhanced by smaller ancillary studies of specific aspects. Plans for such studies should, however, be discussed and agreed in advance with the Management Group. Details of all satellite studies are outlined in Appendix VIII.

10. INDEMNITY

The UKUFF study is sponsored by the University of Oxford. Indemnity and/or compensation for negligent harm arising specifically from an accidental injury for which the University is legally liable as the Research Sponsor will be covered by the University of Oxford.

The University of Oxford have authority to audit the process of the UKUFF trial. Authorised University staff may review aspects of the trial, such as; the consenting process, data collection and storage. UKUFF state that a period of 10 working days notice must be given before these reviews occur.

The NHS will owe a duty of care to those undergoing clinical treatment, with Trust Indemnity available through the NHS Litigation Authority Scheme.

11. PUBLICATION

The success of the trial depends entirely on the wholehearted collaboration of a large number of health care workers. For this reason, chief credit for the trial will be given, not to the committees or central organisers, but to all those who have wholeheartedly collaborated in the trial. The trials' publication policy is described in Appendix IX. The results of the trial will be reported first to trial collaborators. The main report will be drafted by the UKUFF Management Group, and the final version will be agreed by the Trial Steering Committee before submission for publication, on behalf of the UKUFF collaborators.

To safeguard the integrity of the main trial, reports of satellite studies will not be submitted for publication without prior agreement from the UKUFF Management Group.

We plan to maintain interest in the study by publication of UKUFF newsletters at three monthly intervals for collaborators and annually for participants. The newsletters will inform their audience of how the study and recruitment is progressing and any relevant interim results. UKUFF have deemed it important to communicate with the collaborators so that common problems may be addressed and protocol adherence may be monitored.

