5.3 Statistical analysis

Reflecting the possible clustering in the data, the outcomes will be compared using multilevel models, with adjustment for minimisation variables and participant baseline values. Statistical significance will be at the 2.5% level with corresponding confidence intervals will be derived. All participants will remain in their allocated group for analysis (intention to treat). Comparisons (i) and (ii) will be based upon the respective direct randomised evidence only. For comparison (iii), a meta analysis will be used to combine the results from the direct comparison (using stratum A) and an indirect comparison (using strata B and C). A secondary analysis will investigate the impact of surgical expertise level (learning curve effects)¹⁷. All study analyses will be according to a statistical analysis plan that will be agreed in advance by the Trial Steering Committee. A single main analysis will be performed at the end of the trial when all follow up has been completed. An independent Data Monitoring Committee (DMC) will meet early in the trial to agree its terms of reference and other procedures and will review confidential interim analyses of accumulating data at least annually as directed.

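### Section 11 lets the newsletters carry interim results without limit, which conflicts with the confidentiality rule in sections 7.6.1 and 5.3

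*Protocol*

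**What the plan says.** Three parts of the protocol bear on who may learn interim results.

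- **Section 11 (Publication)** plans "publication of UKUFF newsletters at three monthly intervals for collaborators and annually for participants". On content it says: "The newsletters will inform their audience of how the study and recruitment is progressing and any relevant interim results".
- **Section 7.6.1 (Data Monitoring Committee)** says that, during recruitment, "interim analyses will be supplied, in the strictest confidence, to the data monitoring committee". If the DMC judges its two criteria met, it advises the Steering Committee. The text goes on: "The Steering Committee can then decide whether or not to modify intake to the trial. Unless this happens, the Steering Group, Management Group", and then "consultant surgeons and study office staff (except those you supplied the confidential analyses) will remain ignorant of the interim results". The words in brackets evidently mean the staff who supplied the analyses.
- **Section 5.3 (Statistical analysis)** says the DMC "will review confidential interim analyses of accumulating data at least annually as directed". It plans one main analysis, after all follow-up is complete.

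**The concern.** Sections 11 and 7.6.1 use the same term, interim results. Section 11 would send them to collaborators. Section 7.6.1 says the consultant surgeons, who are collaborators, must not know them. A trial team following section 11 as written could breach section 7.6.1.

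The stakes come from the design. Participants and surgeons are told the allocation by letter (sections 3.4.1 and 3.4.2). The primary outcome is the Oxford Shoulder Score at 24 months (section 5.1), and outcomes are self-completed (section 4.1). Surgeons assess eligibility and introduce the trial to patients (sections 3.3.1 and 3.3.2). Rest then Exercise participants are also placed on the surgical waiting list (section 3.4.2). Early results by arm could therefore affect whom surgeons approach, whether participants keep to their allocation, and how they score their shoulder later. The difference the trial is built to detect is 3 points, 0.33 of a SD (section 6.1), so a modest shift in reporting would matter. Results that have been circulated cannot be recalled.

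**Working it through.** The plan gives no figure to reproduce. The check sets the passages side by side and adds one look at the timeline.

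1. **Are surgeons newsletter readers?** Section 11 sends the three-monthly issue to collaborators. Section 7.2 refers to collaborating clinicians, and section 7.2.1 has the lead surgeon represent the centre at collaborators meetings. So yes.

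2. **Does the newsletter clause mean more than progress news?** The sentence already lists study progress and recruitment, then adds interim results as a further item. Read naturally, that item is something else. No section restricts it to pooled, baseline or process data.

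3. **Who must not know interim results?** Section 7.6.1 names four groups: the Steering Group, the Management Group, consultant surgeons and study office staff. It makes one exemption (staff who supplied the analyses) and has one release route (DMC advice on which the Steering Committee acts). Section 11 mentions neither.

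4. **What about participants?** They are not among the four groups. For them the conflict is indirect: analyses supplied in strict confidence (7.6.1) and described as confidential (5.3) cannot also be circulated to participants.

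5. **Could results reach people whose outcome is still to come?** Inputs from section 7.1: recruitment in months 4 to 30; 24-month follow-up completed in months 28 to 54.
   - First 24-month scores: 4 + 24 = month 28. Last: 30 + 24 = month 54.
   - Overlap of recruitment with 24-month data: 30 − 28 = 2 months. Interim results during recruitment would therefore be almost entirely earlier data. The 12-month scores, for example, start at 4 + 12 = month 16.
   - Results circulated at any time before month 54 could reach participants who have not yet given their primary outcome.

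Steps 1 to 3 establish the conflict for surgeons from the wording alone. Step 4 extends it to participants by inference. Step 5 shows that exposure before the primary outcome is possible, not that it will occur.

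**The case against.** The best defence is that section 11 never says comparative, by-arm or outcome data. Its wording is conditional (only what is relevant), and the stated purpose of the newsletters is to keep up interest, deal with common problems and monitor adherence to the protocol. If section 7.6.1 is obeyed, most of the people who might write a newsletter have no by-arm results to print. Pooled or process results would then satisfy both sections.

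This shows that a harmless intention is plausible. It does not remove the conflict, because section 11 states no such limit and uses the very term that section 7.6.1 reserves.

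Some stronger readings are tempting, and the document does not support them:

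- **Only the DMC may see interim results.** Section 7.6.1 exempts the staff who supply the analyses and contains a release clause.
- **Section 7.3.3 is a second contradiction**, because interim reports "will be completed in collaboration with all teams and coordinated by the trial managers in Oxford and Aberdeen". Collaborating on or coordinating a report does not require sight of by-arm outcomes; a trial manager can coordinate a DMC report without seeing its comparative part. The DMC's terms of reference are in Appendix XI, which is not shown.
- **The number of newsletter issues measures the problem.** Such a count would cover every issue, whereas the text promises only relevant results. How many issues would carry any is unknown.
- **Bias is certain.** It depends on by-arm release, which the protocol does not state.

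**Conclusion.** The point holds as a conflict between stated rules. Section 11 allows interim results to go, without limit, to an audience that includes people section 7.6.1 keeps ignorant of them, and section 5.3 calls the underlying analyses confidential. This is not detail left to a statistical analysis plan: the protocol itself states both rules.

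For consultant surgeons the conflict is direct. For participants it rests on the confidentiality wording. The risk of bias is an inference from open allocation and a self-completed primary outcome, and it assumes that outcome results by arm would be released before follow-up ends. The protocol gives no basis for a numerical size. The correction is still worth making before the first newsletter, because it costs almost nothing and a disclosure could not be undone.

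**What to change.** In section 11, delete the closing clause of the newsletter sentence, the one that adds interim results. Put in its place a statement that, until the main analysis, newsletters to collaborators and participants carry only recruitment, retention and procedural news and no outcome data by arm, and that any earlier release follows the DMC and Steering Committee route in section 7.6.1.

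Section 7.3.3 need not change on this account. The cost is a sentence or two of protocol text, with no effect on patients, staffing, procedures or sample size.
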